3.2 Primary Study Endpoints

Endpoint 1: Difference between transfer methods in time for transfer.

Endpoint 2: Difference between transfer methods in number of staff involved in transfer.

Endpoint 3: Difference between transfer methods in proportion of transfers following the OSHA mandate of no more than 35 lbs. lifted per staff member (lbs. lifter per staff member calculated as: weight of patient in lbs. divided by number of staff involved in transfer).

Endpoint 4: Paired difference in satisfaction scores (satisfaction with current transfer method and with SimPull) on staff questionnaires.

Endpoint 5: Paired difference in self-rated risk of injury (with current transfer method and with SimPull) on staff questionnaires.

4 Subject Selection, Enrollment and Withdrawal

Patient selection will be based on set inclusion and exclusion criteria of patients scheduled for procedures in the cardiac catheterization and electrophysiology procedural area. If the patient meets eligibility requirements, consent will be obtained using a written consent process. **The Principal Investigator and Co-Principal Investigator or study members** with recorded conflict of interest do not have consenting privileges and will not participate in the recruitment or consenting process. Using REDCap, the study team will enter data based off transfer observations. If patient consents and no IRB approved study member is available to perform the transfer, the patient will be excluded from the study. If the patient meets inclusion criteria, the clinical research coordinator will validate that a study member is present to transfer the patient prior to consent,. Enrollment will begin with the first 50 patients using the current method of transfer-followed by the pre-survey of staff. Staff will then receive training on the SimPull transfer device and the next enrolled 50 patients will be transferred with SimPull; followed by post-survey of staff. Study members are defined as employees (registered nurses and technicians) of Mayo Clinic assigned to the cardiac catheterization and electrophysiology procedural areas.

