1.2 Investigational Device

SimPull is an automated lateral transfer device that will be used in the catheterization laboratory (cath lab) and electrophysiology laboratory (EP lab) throughout the pilot study. SimPull can complete a lateral transfer in two minutes by one user with zero work force allowing for a removal of the risk of injury while also providing 20-minute reduction in time per transfer. The device is comprised of several important components. The clamp, a unique barbell design utilizes a slip knot to engage to common bed sheets which are readily available under patients. The clamp is attached to an easily cleaned Biothane strap, which feeds into the

motor. The motor generates a pull force allowing up to 500 lbs. of patient weight to be transferred. The motor is housed in a unit, protecting the user, and providing a user interface with clear operating directions. A handheld remote with safety switches is incorporated to ensure staff can guide the patient, the device transfers the patient bearing nearly 100% of the patient's weight. The device utilizes an adjustable feature that allows the height of the device to match the frame of most typical hospital surfaces. The SimPull bumper has two positions, regular, and extended. Once the bumper is in the preferred position, the bumper lock should be engaged and remain locked for the duration of the transfer. The device is the size of a large vacuum on casters that can swivel 360 degrees, making it easy for one person to use and move about floors.

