1.4 Study Rationale and Risk Analysis (Risks to Benefits Ratio)

1.4.1 Study Rationale

The SimPull is a standalone lateral patient transfer device that can be used in environments with limited ceiling access and confined spaces in the acute care setting. The current available products to support lateral transfers, all have the same problem; they require a separate product for the patient to be on top of during transfer. To get patients on these transferrable surfaces is an entirely manual process referred to commonly as “log-rolling” must be performed. This manipulation is attributable to up to 50% of injuries related to lateral transfer. Even with these products available, nurses sustain more injuries than any other profession in any other industry and patient transfer, specifically lateral transfer is a major contributor. When nurses sustain these injuries, it makes them vulnerable to further injury, sometimes unable to participate in transfers post-injury. This creates additional burden and increased risk to uninjured staff as they’re held accountable to do the same transfers without support from injured staff.

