5.1 Description

SimPull is comprised of several important components. The clamp, a unique barbell design utilizes a slip knot to engage a common bed sheet. The clamp is attached to a Biothane strap, which feeds into the motor. The motor generates a pull force allowing 500 lbs. of patient weight to be transferred. The motor is housed in a unit, protecting the user, and providing a user interface with clear operating directions. A handheld remote with safety switches is incorporated to ensure staff can guide the patient as necessary with two hands, the device transfers the patient bearing nearly 100% of the patient's weight. The device utilizes an adjustable feature that allows the height of the device to match the frame of any hospital surface. The SimPull bumper has two positions, regular, and extended. Once the bumper is in the preferred position, the bumper lock should be engaged and remain locked for the duration of the transfer. The lock is an orange handle located underneath the bumper. The height of the bumper can be changed using the twist knob located in the back right of the bumper. Slide the bumper to the height needed and use the twist knob to lock the bumper into place. The device is the size of a large vacuum on casters that can swivel 360 degrees, making it easy for one person to use and move about floors.

The SimPull device will be stored in the cardiac catheterization and electrophysiology lab. The device can be cleaned with standard hospital disinfecting wipes.

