6.1 Sample Size Determination

Power estimate for feasibility outcomes

A sample size of 50 per transfer type (current method vs. SimPull) is estimated to achieve greater than 99% power to reject the null hypothesis of no difference in time to transfer using a two-sided two-sample equal variance t-test, assuming a mean time for transfer of 7 minutes under the current method and 3 minutes using SimPull, a standard deviation in both groups of 3.5 minutes, and a significance level of 0.5. A sample size of 50 transfers per type is estimated to achieve greater than 99% power to reject the null hypothesis of no difference in number of staff using a two-sided two-sample equal variance t-test, assuming a mean of 5 staff involved in transfer under the current method and 2 staff using SimPull, a standard deviation in both groups of 0.5, and a significance level of 0.5.

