6.2 Statistical Methods

Descriptive Statistics

Patient and transfer characteristics will be descriptively summarized by transfer type. Staff questionnaires will be descriptively summarized. The difference between transfer methods in time for transfer and number of staff involved in transfer will be tested using two-sample t-tests. A possible secondary analysis would test differences using a regression model adjusting for differences in patient or transfer characteristics. The difference between transfer methods in proportion of transfers following the OSHA mandate of no more than 35 lbs. lifted per staff member will be tested using a Chi-square or Fisher's exact test. A possible secondary analysis would test differences using a regression model adjusting for differences in patient characteristics. The paired differences in mean staff satisfaction scores and self-rated risk of injury scores will be tested using paired tests.

Primary Hypothesis:

SimPull lateral transfer device is a more efficient and safe method of lateral patient transfer than current methods of lateral transfer.

By recording patient weight and the number of clinicians engaged during manual transfers we can calculate the force needed by each individual. Example: Patient weight: 265 lbs., five clinicians: 53 lbs. per clinician (51% higher than the 35 lb. OSHA mandate). This data collection allows risk assessment of clinician injury during transfer in each location by

establishing weight pulled by clinicians and the number of transfers per day. Using this we can also forecast force required and risk of injury over time. Time to complete in seconds will be recorded for each lateral transfer.

Secondary Hypothesis:

Use of the SimPull device for lateral transfers will increase staff satisfaction and be a preferred method of lateral patient transfer.

Data collected pre and post SimPull implementation

- Employee Satisfaction
- Employee Perception of Injury Risk

Staff/Clinician Participant Survey:

Part 1 of Survey – Pre-Training

1. What is your preferred method for performing lateral patient transfers?
 - a. Manual, Assisted, Ceiling Lift, or Air Mattress
2. Do you feel at risk of injury performing lateral patient transfers?
 - a. No Risk, Minimal Risk, Neutral, Some Risk, High Risk
3. How likely do you feel you are to be injured during lateral patient transfer?
 - a. Not at all likely, Not Likely, Neutral, Likely, Very Likely

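### Endpoint 3 divides full patient weight by staff for both methods and has no load rule for SimPull, so with similar weights and fewer SimPull staff it can only tilt against the device

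*Combined protocol and SAP*

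**What the plan says.** Section 3.2 lists five primary endpoints. Endpoint 2 is the number of staff per transfer. Endpoint 3 is the proportion of transfers within the 35 lb limit, with load per person defined as "lbs. lifter per staff member calculated as: weight of patient in lbs. divided by number of staff involved in transfer". No exception is made for either method. Section 6.2 plans a between-method test: the "proportion of transfers following the OSHA mandate of no more than 35 lbs. lifted per staff member will be tested using a Chi-square", with Fisher's test as the alternative.

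Other sections bear on that definition:

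- Section 1.2 says "SimPull can complete a lateral transfer in two minutes by one user with zero work force" and that "the device transfers the patient bearing nearly 100% of the" patient's weight. Section 5.1 repeats the second statement and says the remote is there "to ensure staff can guide the patient as necessary with two hands".
- Section 6.1 plans the study "assuming a mean of 5 staff involved in transfer under the current method and 2 staff using SimPull".
- Section 6.2 introduces the load calculation with "By recording patient weight and the number of clinicians engaged during manual transfers we can calculate the force needed by each individual". Its one worked example is a 265 lb patient moved by five clinicians.
- Section 1.4.1 says of existing transfer aids: "To get patients on these transferrable surfaces is an entirely manual process referred to commonly as" log-rolling. The plan does not say how a current-method transfer that uses an aid is scored, or how often aids are used in these labs.

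**The concern.** Dividing body weight by head count is a rough measure of load when staff move the patient. When a motor moves the patient and staff guide, it charges them with a load that the protocol says they do not carry. The fewer the staff, the larger the charge, so the staff reduction that counts as success on Endpoint 2 counts as harm on Endpoint 3.

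The wording in 6.2 about manual transfers hints that the formula was not meant for SimPull. On that reading the 50 SimPull transfers have no defined score, yet the same section tests them against the current method. Neither reading gives a usable comparison.

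This matters because Endpoint 3 is the only primary endpoint on staff load that is not self-rated, and the primary hypothesis in 6.2 claims safety as well as efficiency. If the gap stays open, either the literal result is reported or a rule is chosen after the data are seen.

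**Working it through.** **The plan's own figures.** 265/5 = 53 lb and 53/35 − 1 = 51%, as printed in 6.2. 200/35 = 5.7, hence the six clinicians in 1.1. For staff number (5 vs 2, SD 0.5, 50 per group) the t-test has power above 99%, as 6.1 states, at the printed significance level of 0.5 and also at 0.05.

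**Literal thresholds.** A transfer complies if weight ≤ 35 × staff: 35 × 5 = 175 lb, 35 × 2 = 70 lb, 35 × 1 = 35 lb. A 200 lb patient scores 200/5 = 40 lb per person under the current method and 200/2 = 100 lb with SimPull. The 265 lb patient scores 53 and 265/2 = 132.5 lb. If weights have the same distribution in both groups, fewer staff can only lower expected compliance. The direction therefore needs no assumption about the SD; only its size does.

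**Size.** From the documents: 50 per group, mean staff 5 and 2, staff SD 0.5 (6.1). The mean weight of nearly 200 lb is a general remark in 1.1 and not a figure for these labs, so it is varied. Assumed: normal weights with SD 35-50 lb, and Fisher's test at two-sided 0.05.

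Let k be the staff count, normal and rounded to a whole number of at least 1. Compliance is p = Σ P(k) × Φ((35k − mean)/SD). At mean 200 and SD 50:

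- Current, with P(4) = P(6) = 0.157, P(5) = 0.683, P(3) = P(7) = 0.001: 0.157 × Φ(−1.2) + 0.683 × Φ(−0.5) + 0.157 × Φ(0.2) + 0.001 × [Φ(−1.9) + Φ(0.9)] = 0.018 + 0.211 + 0.091 + 0.001 = 0.321.
- SimPull, with P(1) = 0.159, P(2) = 0.683, P(3) = 0.157: 0.159 × Φ(−3.3) + 0.683 × Φ(−2.6) + 0.157 × Φ(−1.9) = 0.0001 + 0.0032 + 0.0045, about 0.008.

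At SD 35 the two proportions are 0.267 and 0.0007. Taking the number compliant in each group as Binomial(50, p) and applying Fisher's test to every possible table gives the chance of a significant result against SimPull (range over SD 35-50, 2 SimPull staff):

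| Mean weight | 5 current staff | 4 current staff | 3 current staff |
|---|---|---|---|
| 180 lb | about 100% | 79-87% | 0-10% |
| 200 lb | 99.6-99.8% | 12-54% | 0-1% |
| 220 lb | 66-93% | 0-11% | about 0% |

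Over 3 to 6 current staff, means of 180-220 lb and these SDs, the chance of a significant result favouring SimPull is below 0.001%.

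**Unequal weights.** Section 5.2 makes the groups sequential and non-randomised, so weights may differ. If SimPull patients average 40 lb lighter (5 vs 2 staff, SD 35 and 50), the chance of significance against SimPull is still 94-97% at a current-group mean of 200 lb and 61-78% at 220 lb.

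**The case against.** The strongest defence is that the authors plainly did not mean to charge SimPull staff with the full weight: the endpoint speaks of pounds lifted, 1.2 claims no work force, and 6.2 mentions manual transfers. That is probably right about intent. But 3.2 prints one formula for both methods, and no section supplies another for SimPull, so the scoring rule still has to be written.

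A second objection is that a corrected rule may do no better, and much of this stands. If hand guiding counts as manual handling, guided SimPull transfers return to weight divided by about 2 and the flaw comes back. If guiding does not count, a device that works as described complies largely by definition. The fix must disclose both.

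Third, this is a pilot. The primary objective in 2.1 is efficiency, and only Endpoints 1 and 2 carry a power statement. That limits the damage but does not remove it, because Endpoint 3 is listed as primary and is formally tested.

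A reader might infer that the trial is bound to report SimPull as significantly worse. The documents do not support that. The high probabilities rest on 5 current staff, which is a planning figure. Section 1.1 itself says staff ignore the limit to stay on schedule, so actual numbers could be lower. With about 3 current staff both groups sit near zero and the endpoint is merely uninformative.

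**Conclusion.** The defect holds and should be corrected before data collection. As written, Endpoint 3 either scores SimPull by a load that the protocol says staff do not bear, or leaves SimPull transfers unscored. With similar weights and fewer SimPull staff, the literal formula can only favour the current method. At 5 versus 2 staff the chance of a significant adverse result is 99.6-99.8% at a mean of 200 lb and 66-93% at 220 lb. These figures assume normal weights with SD 35-50 lb, staff SD 0.5, 50 per group and Fisher's test at 0.05. They drop sharply with fewer current staff.

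Two stronger inferences should be resisted. The flaw does not reach the time or staff-count endpoints or the sample size, which do not use this formula. Nor does removing it show that SimPull is safer: with the load rule changed, the result follows largely from the definition, and no force is measured in either group.

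**What to change.** Before the first current-method transfer, reconcile 3.2 with 6.2:

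- Apply weight divided by staff only to transfers in which staff themselves lift or pull the patient, in either group. Count a transfer as compliant if no staff lifting or pulling was needed, or if weight divided by staff is at most 35 lb.
- Because the endpoint concerns pounds lifted, state that hand guiding while the device moves the patient is neither lifting nor pulling. Fix in advance, with the same rule for both groups, whether log-rolling to place an aid counts.
- Record in REDCap, for every transfer, the method or aid, whether staff lifted or pulled, and whether they only guided.
- Keep the planned chi-square or Fisher test, report weight divided by staff for manual transfers descriptively, and add a sensitivity analysis that counts guided transfers as manual.

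The cost is rewording two sections and up to three form fields, if the transfer form (not in the documents) lacks them. No extra patients are needed.

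Downsides to state openly, all at 5 vs 2 staff, mean 200 lb, SD 35 and 50:

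- The guiding rule sets the direction. If guiding counted as manual (with log-rolling also counted), the chance of significance against SimPull would be 99.6-99.8% when all SimPull transfers are guided and 48-69% when 90% are.
- With guiding excluded, report the result as the share of transfers done without staff lifting or pulling, not as measured force.
- The log-rolling rule matters. Suppose half of current transfers use an aid. If 90% of SimPull transfers need no lifting or pulling, power in favour of SimPull is over 99.9% with log-rolling counted and 79-86% without. If 70% do, it is 97-99% and 4-7%. These shares are assumptions.
- The record is made by an unblinded observer, and weight divided by staff is only a rough proxy for log-roll load.

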4.1 Inclusion Criteria

- Patients weighing less than 500 pounds
- Patients requiring lateral transfer for an invasive cardiac procedure to and from gurney to exam table.
- Patients requiring lateral transfer for an invasive cardiac procedure to and from exam table to gurney.
- Patient does not have compound fractures or cervical fractures present.
- Patient does not have skin damage or open wounds to the dorsal cavity.
- Patient or legally authorized representative (LAR) must be able/present to sign consent.

4.2 Exclusion Criteria

- Patients exceeding the SimPull maximum weight of 500 pounds
- Patients who do not require lateral transfer for an invasive cardiac procedure to and from gurney to exam table.
- Patients who do not require lateral transfer for an invasive cardiac procedure to and from exam table to gurney.
- Patient has compound fractures or cervical fractures present.
- Patient has skin damage or open wounds to the dorsal cavity.
- Patient or legally authorized representative (LAR) are unable/present to sign consent.

4.3 Subject Recruitment, Enrollment and Screening

The Research Coordinator screens patients scheduled for procedures in the cardiac catheterization and electrophysiology procedural area in for inclusion and exclusion criteria. Potential subjects who meet inclusion criteria will be consented to participate in the study by the Research Coordinator. Potential subjects are given the opportunity to ask questions prior to consenting. Potential subjects will be enrolled by the Research Coordinator after information is given to the patient in the form of a handout.

4.4 Early Withdrawal of Subjects

4.4.1 When and How to Withdraw Subjects

Subjects may choose to withdraw from the study (withdrawal of consent) at any time prior to use of the SimPull for lateral transfer. Any subject that withdraws their consent will be replaced so data is collected on 50 total subjects per transfer method.

4.4.2 Data Collection and Follow-up for Withdrawn Subjects

No follow-up is necessary for subjects that withdraw their consent.

5 Study Device

5.1 Description

SimPull is comprised of several important components. The clamp, a unique barbell design utilizes a slip knot to engage a common bed sheet. The clamp is attached to a Biothane strap, which feeds into the motor. The motor generates a pull force allowing 500 lbs. of patient weight to be transferred. The motor is housed in a unit, protecting the user, and providing a user interface with clear operating directions. A handheld remote with safety switches is incorporated to ensure staff can guide the patient as necessary with two hands, the device transfers the patient bearing nearly 100% of the patient's weight. The device utilizes an adjustable feature that allows the height of the device to match the frame of any hospital surface. The SimPull bumper has two positions, regular, and extended. Once the bumper is in the preferred position, the bumper lock should be engaged and remain locked for the duration of the transfer. The lock is an orange handle located underneath the bumper. The height of the bumper can be changed using the twist knob located in the back right of the bumper. Slide the bumper to the height needed and use the twist knob to lock the bumper into place. The device is the size of a large vacuum on casters that can swivel 360 degrees, making it easy for one person to use and move about floors.

The SimPull device will be stored in the cardiac catheterization and electrophysiology lab. The device can be cleaned with standard hospital disinfecting wipes.

5.2 Method for Assigning Subjects to Treatment Groups

Patient selection will be based on set inclusion and exclusion criteria of patients scheduled for procedure in the cardiac catheterization and electrophysiology procedural area. If the patient meets eligibility requirements, consent will be obtained using a paper consent process.

Patients will not be randomly assigned to treatment group. The first 50 patients (or greater than 50 if there are withdrawals) will have the current method of transfer. The next 50 patients (or greater than 50 if there are withdrawals) will have the SimPull device for transfer.

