3.1 General Design

The methods for this pilot study are fundamentally straightforward; preliminary data collection, pilot and data collection, review, and publish. Data of 50 patients using current methods of lateral transfer and 50 patients using the SimPull device for lateral transfer will be

collected. Employees in the cardiac catheterization and electrophysiology procedural areas have been offered the opportunity to complete IRB study member requirements. Employees in the cardiac catheterization and electrophysiology procedural areas will be completing a survey for the 100 lateral transfers. Employees in the cardiac catheterization and electrophysiology procedural areas that have direct patient care responsibilities, completed IRB requirements, have been added as study members on the IRB application, and received hands on education on proper use of the SimPull device, may perform lateral transfers using the SimPull device and complete study surveys. Employees in the cardiac catheterization and electrophysiology procedural areas that have not completed IRB requirements and have not been added as study members on the IRB application, will perform standard of care for lateral transfers and will not complete study surveys. All study members will receive instruction prior to the study on how to complete the survey. The Principal Investigator and Co-Principal Investigator do not have consenting privileges and will not participate in the recruitment or consenting process.

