11.3 Subject Stipends or Payments

No payments or reimbursements will be distributed in exchange for participation in this study.

12 Publication Plan

The data will be published in one report but as unique locations, allowing analysis of unique benefit or drawback in a specific location, aiming to prove feasibility in each.

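### The switch of transfer method is counted over both laboratories together, so a shift in the cath/EP mix between phases would bias the pooled comparisons, and the by-location results have no assured size

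*Combined protocol and SAP*

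**What the plan says.** Section 1.2 places the device in two areas: it "will be used in the catheterization laboratory (cath lab) and electrophysiology laboratory (EP lab) throughout the pilot study". Section 5.2 fixes the assignment rule. It excludes randomisation and goes by enrolment order instead: "The first 50 patients (or greater than 50 if there are withdrawals) will have the current method of transfer". SimPull is then used for the 50 enrolled after them, again with an allowance for withdrawals. Section 4 describes the same order. Section 4.4.1 handles withdrawals per method: "Any subject that withdraws their consent will be replaced so data is collected on 50 total subjects per transfer method". No section gives a quota, a minimum or a separate switch point for either laboratory.

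Section 6.2 compares time and number of staff by two-sample t-tests, and OSHA compliance by a Chi-square or Fisher's exact test. Regression adjustment is mentioned only as an option, and laboratory is not named as a covariate. The power statement in Section 6.1 covers only the pooled 50 against 50.

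Section 12 nevertheless states: "The data will be published in one report but as unique locations, allowing analysis of unique benefit or drawback in a specific location", and goes on to aim at showing feasibility in every location. Section 6.2 also expects to assess clinician injury risk by location. The documents do not define location. In a single-site study run in these two areas, cath laboratory against EP laboratory is the reading that fits.

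**The concern.** In a sequential design, whatever changes between the phases is mixed with the method effect. Laboratory mix is one such factor, it is known at screening, and the plan leaves it free.

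The protocol itself contains a way for the mix to move. Under Section 4 a patient enters only if an approved study member is available for the transfer. Under Section 3.1 a SimPull transfer also needs a member with hands-on training, which Section 4 places between the phases. The staff pool that decides who can be enrolled may therefore change at the switch, and nothing makes it change equally in the two laboratories.

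Two things are at stake. If transfer time, staffing or patient weight differs by laboratory, a shift in mix enters the pooled estimates of Endpoints 1-3 directly. And the by-location results have whatever precision the enrolment order happens to leave them.

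**Working it through.** **Inputs from the documents.** 50 patients per method (Sections 3.1 and 5.2). For time: means 7 and 3 min, SD 3.5 min, two-sided two-sample t-test. For staff: means 5 and 2, SD 0.5 (Section 6.1). The printed significance level is 0.5; I use 0.05 below as an assumption.

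**Inputs not in the documents.** The share of patients from each laboratory, its change between phases, and the difference between laboratories in time or staffing. These are assumed and shown as ranges.

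**The plan's own figure.** Pooled SE for time = 3.5 × √(2/50) = 0.70 min. Power for 4 min is 99.99% at 0.05 and higher at 0.5. For staff, SE = 0.5 × √(2/50) = 0.10 and power for a difference of 3 is effectively 100%. The stated figure of more than 99% reproduces.

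**Bias in the pooled comparison.** With the same method effect in both laboratories, bias = (EP share in the SimPull phase − EP share in the current-method phase) × (EP mean − cath mean).

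- Time, assumed 40-point shift: 0.4 × 1 = 0.4 min to 0.4 × 3 = 1.2 min, that is 0.6 to 1.7 SE.
- Staff, same shift and an assumed laboratory difference of 0.5 to 1 person: 0.4 × 0.5 = 0.2 to 0.4 × 1 = 0.4 staff, against a planned difference of 3.
- OSHA proportion: the same product, with the laboratory difference in compliance. The documents give nothing to put in.

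**Would it overturn the result?** If the largest of these time biases worked against SimPull, 4 − 1.2 = 2.8 min would remain. At 50 against 50 this is 2.8/0.70 = 4.0 SE, with power about 98%.

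**Size of the by-location cells.** Let s be the smaller laboratory's share, stable over both phases. Each of its two cells is Binomial(50, s). The half-width is t(0.975, 2n−2) × 3.5 × √(2/n) at the expected cell size n = 50s, and power is from the noncentral t for 4 min.

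| Assumed s | Expected per cell | Chance that a cell is below 5 | 95% half-width | Power |
|---|---|---|---|---|
| 10% | 5 | 68% | 5.10 min | 36% |
| 20% | 10 | 3.7% | 3.29 min | 68% |
| 30% | 15 | 0.03% | 2.62 min | 86% |
| 50% | 25 | about 0 | 1.99 min | 98% |

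**Comparing the laboratories with each other.** Even at 25 per cell, the SE of the difference between the two method effects is 3.5 × √(4/25) = 1.40 min. A difference of about 2.80 × 1.40 = 3.9 min is needed for 80% power, nearly the whole planned effect.

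**The case against.** The case for leaving the plan alone has several parts.

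**The pooled effect is large.** The planned 4 min and 3 staff survive any shift considered here. This stands, and it limits the point to the accuracy of the estimates.

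**Chance imbalance is not bias.** With a half-and-half mix, the share difference has SD √(2 × 0.5 × 0.5/50) = 0.10, so chance alone gives up to about ±20 points. A reader might count this as bias. It is random error with expectation zero, already within the 0.70 min if 3.5 min is the SD over both laboratories. Only a systematic shift counts, and the documents neither show nor exclude one.

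**The by-location aim is loosely stated.** It appears in a publication plan, location is undefined, and Section 6.2 specifies no test by laboratory. So within-laboratory power should not be demanded of a pilot. This stands, but Section 12 still sets out to prove something in each location, with no assured number of patients there.

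**The analysis could handle it.** Section 6.2 summarises patient and transfer characteristics by method and permits regression. Naming laboratory as a covariate would address the mix without restricting enrolment. As written, the regression is optional and laboratory is not named, and adjustment would not help a sparse cell.

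**Equal quotas are not a complete cure.** A reader might infer that 25 per laboratory per method settles everything. If one laboratory supplies 20% of patients, filling 25 from it takes about 0.5/0.2 = 2.5 times as long as enrolling 50 overall, against the two months in Section 1.5. Closing the busier laboratory early would also widen the calendar gap between its two phases.

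**Conclusion.** The gap is real, and closing it is a cheap improvement. The method switches on a count over both laboratories, the main tests are unadjusted, and the design does not hold the laboratory mix constant between phases. A systematic shift would bias Endpoints 1-3. For time this is 0.4-1.2 min under an assumed 40-point shift and an assumed laboratory difference of 1-3 min, against an SE of 0.70 min. That would distort the estimate and its interval, but is unlikely to overturn the planned 4-minute effect.

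A reader might also infer that one laboratory's cells will be nearly empty. The documents do not support that: cells below 5 are likely only at a share of about 10% or less, are already unlikely at 20%, and no share is given. Strongly lopsided cells such as 10 against 40 or 5 against 45 within one laboratory would need its share to swing by 60 or 80 points between phases, for which the documents offer no basis. What can be said is that the by-location results have no assured cell size.

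**What to change.** In Section 5.2, set the SimPull-phase quota for each laboratory equal to the number enrolled from it in the current-method phase, and close a laboratory to that phase when its quota is full. In Section 4.4.1, replace withdrawals from the same laboratory. The total stays at 100. Use 25 per laboratory per method only if the laboratories' case volumes allow it within two months.

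Matching removes the laboratory-mix bias. It does not remove before/after confounding such as calendar time or learning, and it does not enlarge a small laboratory's cells: 5 in the first phase means 5 in the second. Sections 6.2 and 12 should therefore say that by-location results are descriptive, given with confidence intervals and cell sizes.

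The cost is a wording change, a running tally by the research coordinator, and possibly slightly slower enrolment at the end of the SimPull phase while the last quota fills.
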